3.4. Inclusion of Minorities

Adult patients of all races and ethnic groups will be considered for study participation.

4. Registration Procedure

All patients who have signed informed consent and met the eligibility criteria will be registered in the Research Electronic Data Capture (REDCap) system and will be issued a study specific ID number.

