4.2. Informed Consent

Authorized study personnel should fully explain the scope of the study to each patient before obtaining informed consent. When obtaining informed consent, study personnel should:

First: Confirm that the patient is a potential candidate for study participation.

Next: Obtain dated and signed informed consent document.

Finally: Confirm that the patient is eligible as defined in Sections 3.2 and 3.3 (Inclusion/Exclusion Criteria).

5. Study Design

This trial will recruit primary care patients at David Grant Medical Center (DGMC) that have at least one risk factor for CHD or T2D. Enrolled subjects will be randomized to one of four groups:

1. Standard Risk Assessment (SRA) only;
2. SRA plus Health Coaching (SRA+HC);
3. SRA plus Genetic Risk Counseling (SRA+GRC); ***or***

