Samples will be sent to Duke University Clinical Molecular Diagnostics Laboratory, which is CLIA-certified. DNA extraction will be performed as well as real time PCR allelic discrimination assays for RS7903146, RS1801282, RS5219, and RS10757274 (Appendix P.). Results (genotyping of alleles for SNPs of interest) will be returned by subject studyID number to the site research staff for entry into the REDCap database. Remaining blood samples will be retained by the lab until the end of the study, at which time they will be discarded.

Standard Risk Assessment (SRA) for CHD and T2D (need to take place no later than 4 weeks post randomization)

The SRA has been developed for this study based on the Framingham risk assessment and other known risk factors for CHD and T2D. The SRA consists of: FBG, age, gender, BMI, total cholesterol, HDL, BP, family history (number of first-degree relatives who have CHD (and age at diagnosis) or T2D, self-reported), and smoking (self-reported). A Framingham Risk Score and Diabetes Risk Score will be calculated for each patient along with other well-validated CHD and T2D risk factors, and all will be reviewed at the risk counseling visit. This method of presenting genetic risk data to patients has successfully been used for over 400 clinical study patients to be used by the provider (Appendix K., L., M., N.).

Health Coaching(HC) Intervention. Upon completion of their individual SRA Visit, participants in the two groups that include health coaching will be assigned to a trained health coach for a period of 5 months (n=200). At the SRA, the participant will fill out a “Current & Desired States Form” (Appendix C.). Then the participant will be given a folder containing information about what HC is, how the calls will be structured, and preparation materials for the calls (Appendix E.). An initial telephone call (60-75 minutes in length) with the coach will consist of a discussion on the role of the health coach and participant, the logistics of the sessions, and a discussion about the participant’s self-assessment of health perceptions and goals. This self-assessment creates the foundation for the personalization of the behavioral intervention. From this point, the

Genetic Risk Testing and Health Coaching for CHD and T2D

Duke IRB# Pro00039569 NCT01884545

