Pattern	Type I error rate	Power	Within Person Correlation	Sample Size per Group	Total Sample Size
1	.025	.80	.350	25	100
1	.025	.85	.350	27	108
2	.025	.80	.350	44	176
2	.025	.85	.350	49	196
3	.025	.80	.350	56	224
3	.025	.85	.350	63	252

- b. Means for the four groups pooled across time showing JUST the coaching by genetics testing interaction for each pattern.
- c. Examining the health coaching by time and the genetic testing by time interactions. Assuming the same means over time for pattern 2, the means for the two interactions would be as shown in the two tables immediately below.

Health coaching by time interaction for pattern 2

	NO HC	HC
0	0.05	0.05
1.2	0.15	0.5
3	0.275	0.95
6	0.125	1.5
12	0.05	0.85

Genetic testing by time interaction for pattern 2

	No Genetics	Genetics
0	0.05	0.05
1.2	0.225	0.425
3	0.425	0.8

6	0.525	1.1
12	0.225	0.675

d. Results of power calculations when the three way interaction for the groups, as well as the three way interaction for time by health coaching by genetic testing are eliminated. These are the power for detecting the interaction which is the smallest (the genetic testing one).

Pattern	Type I error rate	Power	Within Person Correlation	Sample Size per Group	Total Sample Size
2	.025	.80	.350	43	172
2	.025	.85	.350	49	196

While we will have lost the power to examine a 3-way interaction (health coaching by genetic risk testing by time), with the participants, we will still be able to:

- 1) Examine 2 way interaction effects of health coaching by time and genetic risk testing by time (estimated minimum sample needed 172-196);
AND/OR
- 2) Examine the 2 way interaction of health coaching and genetic risk testing (comparative effectiveness without time point considered in interaction; estimated sample needed 176-196).

Assuming an attrition rate of at most 15% the required minimum sample size is 212.

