The second part of the primary analysis will determine the direct and interactive effects of genetic risk information incorporated with standard CHD/T2D risk counseling and a health coaching intervention for CHD/T2D on metabolic outcomes (fasting blood glucose, SBP, BMI, waist circumference, LDL, triglycerides, total cholesterol) over 12 months. The statistical analysis will be the same as above except that the dependent variables will be fasting blood glucose, SBP, BMI, waist circumference, LDL, triglycerides, and total cholesterol.

To address Aim 2, we will examine the mediating effects of level of CHD/T2D genetic risk (number of risk alleles) and consequent reclassification of FRS in the case of CHD risk (decreased, neutral, or increased) on behavior change (diet, physical activity) at 6 months. The goal of this analysis is to quantify the extent to which subgroups of patients exhibit different levels of change in diet and physical activity behavior at 6 months post randomization depending on reclassification of FRS and T2D risk level. We also want to know if the differences depend on whether or not the genetic results were delivered in the context of health coaching. For these analyses, we will use results from only the two groups of patients randomized to receive genetic testing (n=200). Because we will have only two points in time, we will use the simpler linear regression model, with the dependent variable being either diet or physical activity collected at 6 months post randomization. There will be six independent variables: the outcome measured at baseline (a covariate), the results of the genetic testing (entered as two dummy coded variables), a dummy coded variable to indicate the presence or absence of health coaching, and two dummy coded variables representing the interaction of health coaching and the results of genetic testing. We are particularly interested in comparing the diet and physical activity changes of patients whose genetic test results move their Framingham risk or T2D levels either up or down (based on number of higher-risk alleles) to those whose genetic

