results do not. In our regression analysis, this comparison will be facilitated by creating two dummy coded variables; dummy 1 will be 1 if the patient has ‘low’ risk based on number of risk alleles and zero otherwise. Dummy 2 will be 1 for patients with ‘high’ risk based on number of risk alleles and zero otherwise. When group membership is coded in this way, the regression coefficients (parameters) fit to the data represent differences in adjusted group means. “Adjusted” refers to group differences on outcome measures obtained at 6 months, while statistically eliminating any differences between groups on outcomes at baseline. Thus, the regression coefficient for dummy 1 will reflect the differences in average adjusted outcome at 6 months between patients whose genetics results shifted their risk down and patients whose results did not affect their risk. Similarly, the regression coefficient for dummy 2 will reflect differences in adjusted outcome means comparing patients whose risk shifted up to those whose risk was unaffected by their genetic test results. The interaction components of this model will allow us to assess whether or not these comparisons significantly differ depending upon whether or not the patient received health coaching.

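### The genetic-result groups in the risk-level regression are not randomised and only the baseline outcome is adjusted for, so the two result contrasts are open to confounding and should be reported as adjusted associations

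*Combined protocol and SAP*

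**What the plan says.** Section 5 (Study Design) states what is randomised: "Enrolled subjects will be randomized to one of four groups", defined by genetic risk counselling and health coaching. The genetic result itself is observed, not assigned.

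The regression that Section 8.2 attaches to Aim 2 uses only the two genetic arms. Its terms are specified as follows: "There will be six independent variables: the outcome measured at baseline (a covariate), the results of the genetic testing (entered as two dummy coded variables"; then a coaching indicator and two coaching-by-result products. The coding is by genotype: "dummy 1 will be 1 if the patient has ‘low’ risk based on number of risk alleles and zero otherwise", with dummy 2 defined likewise for high risk. The same section also speaks of reclassification of the Framingham Risk Score (FRS) as a grouping.

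The two coefficients are interpreted as adjusted 6-month differences between patients whose result moved their risk down or up and those whose result left it unchanged. Adjustment is explained as "statistically eliminating any differences between groups on outcomes at baseline". The section does not say that these comparisons are observational.

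On who may enrol, Section 3.4 says: "Adult patients of all races and ethnic groups will be considered for study participation". Section 8.2 lists race/ethnicity among the demographic variables. Section 5.3.2 collects the number of first-degree relatives with either disease, and adds: "A Framingham Risk Score and Diabetes Risk Score will be calculated for each patient". None of these enters the regression. Baseline characteristics are to be described overall and by randomised group, not by result group.

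**The concern.** Patients with low, neutral and high results may differ in more than what they were told. Allele frequencies can vary with ancestry, and carriers of risk alleles may have more affected relatives and may already behave differently for that reason. If the groups are formed by FRS reclassification, only patients close to a risk cut-point can change category, so the groups can also differ in baseline clinical risk.

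A single baseline measurement of the outcome is a noisy record of a person's usual behaviour. Conditioning on it removes only part of a lasting difference between groups. The remainder would appear in the coefficients of dummies 1 and 2 and could be reported as a response to genetic information. Section 8.2 singles out these comparisons as being of particular interest.

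The design offers no internal check. Section 5.3.1 takes blood for genotyping only in the genetic arms, so no patients with a known genotype go uninformed of it. An effect of being told a result cannot be separated from an existing association between genotype and behaviour.

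**Working it through.** The documents give no power, effect-size or error calculation for this regression, so there is no stated figure to reproduce.

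**Inputs from the documents**
- Within-person correlation rho = .350, the value in every row of the Section 8.1 power tables (column "Within Person Correlation").
- Enrolment of 250 (Section 5.1), so about 125 in the two genetic arms. With at most 15% attrition (Section 8.1), 125 x .85 = 106 evaluable. Section 8.2 still gives n=200 for this analysis, which does not match enrolment of 250.

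**Inputs assumed**
- Result split of 25/50/25 (low/neutral/high), outcome SD of 1 at both times, two-sided 5% test. No alpha is stated for this regression.

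**Step 1: share of a stable difference left after adjustment.** With equal variances the slope on baseline equals rho. If groups differ by D at both times and the result has no effect, the adjusted difference is D - rho x D = (1 - rho) x D.

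| rho | share remaining |
|---|---|
| .20 | 80% |
| .35 | 65% |
| .50 | 50% |
| .70 | 30% |
| .80 | 20% |

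**Step 2: precision in the six-term model.** With coaching coded 0/1 and interactions present, each result dummy is a contrast among uncoached patients only, about 106/2 = 53 people. On the assumed split the high group has 13.25 and the neutral group 26.5. The standard error (SE) is

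SE = sqrt[(1 - .35²) x (1/13.25 + 1/26.5)] = sqrt(.8775 x .1132) = 0.315 SD.

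A model without interactions would give sqrt[.8775 x (1/26.5 + 1/53)] = 0.223 SD, but that is not the model in the plan.

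**Step 3: illustrative bias at rho = .35.**
- *By allele count:* .65 x ancestry difference in behaviour (0.2-0.5 SD, assumed) x difference in ancestry share between result groups (0.1-0.3, assumed). Low end .65 x 0.2 x 0.1 = 0.01 SD; high end .65 x 0.5 x 0.3 = 0.10 SD.
- *By FRS reclassification:* gap in clinical risk between reclassified and unchanged patients (0.3-0.9 SD) x behaviour difference per SD of risk (0.1-0.3 SD, assumed) x .65. Low end 0.3 x 0.1 x .65 = 0.02 SD; high end 0.9 x 0.3 x .65 = 0.18 SD. The 0.3-0.9 gap comes from simulating a normal log-risk with genotype shifts of 0.2 or 0.3 SD. It depends on where the cut-points lie and is smaller when they sit near the centre of the risk distribution.

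**Step 4: true size of a nominal 5% test.** Size = P(Z > 1.96 - b/SE) + P(Z < -1.96 - b/SE), with SE = 0.315.

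| bias b (SD) | size |
|---|---|
| 0.01 | 5.0% |
| 0.06 | 5.4% |
| 0.10 | 6.2% |
| 0.12 | 6.7% |
| 0.18 | 8.8% |

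**Step 5: simulation of the six-term regression** (3,000 runs per setting, N = 106 unless stated, no true result effect).
- No stable difference: mean coefficient about 0, rejection rate 4.8%.
- Stable difference of 0.2 SD: rejection rate 6.5%.
- Stable difference of 0.5 SD: mean coefficient 0.32 SD, against .65 x 0.5 = 0.325 expected; rejection rate 17%. This is well above the differences implied in Step 3 and serves only to check the formula.
- A 0.5 SD baseline difference that is not stable but regresses at slope rho (run at N = 200): mean coefficient about 0, rejection rate 5.6%.

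**Step 6: the interaction terms.** Coaching is randomised within each result group. A stable difference that adds equally in coached and uncoached patients cancels from the coaching-by-result coefficients.

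**The case against.** The strongest reply is that the sentence on elimination merely explains what an adjusted mean is. It is limited to outcomes at baseline and does not claim balance on ancestry, family history or clinical risk. In that narrow sense it is correct, because the regression does condition on the observed baseline score. That stands. What fails is the extension to a lasting difference that one score measures imperfectly, or to factors that act on 6-month behaviour by other routes.

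A reader might infer that the result effects *are* confounded. The documents do not support this. They report no difference in diet or activity between genotype groups, no ancestry mix and no link between clinical risk and behaviour. Genotype precedes behaviour, and without a stable difference there is no bias (Step 5).

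A reader might also take it as fact that adjustment removes only 35%. The .350 is a planning value for unspecified standardised outcomes, not an estimate for the diet or activity instruments. The figure also needs equal variances and a fully stable difference.

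Thirdly, the larger biases need groups formed by FRS reclassification, whereas the dummies as written use allele count. That is right, and it confines the allele-count case to a size of about 5-6%. Section 8.2 does name reclassification, however, so the reading cannot be excluded.

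Finally, extra covariates cannot make up for the missing genotypes in the other two arms. This also stands, and it is why the conclusion has to be reworded as well as the model extended.

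**Conclusion.** The point holds as a matter of uncontrolled risk and of interpretation. The contrasts for dummies 1 and 2 compare groups that were not randomised, with one covariate, and the plan does not label them observational. Confounding is possible but has not been shown.

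The likely size is modest: about 5-6% for a nominal 5% test under allele-count coding, and up to about 9% under reclassification. These figures rest on rho = .35, 106 evaluable patients, a 25/50/25 split and the assumed behavioural differences. A higher correlation shrinks the bias. The false-positive rate stays low partly because the contrast is imprecise (SE about 0.315 SD), so the main gain from a change is in what may be concluded.

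The coaching-by-result terms are not affected by an additive stable difference, and the mixed models comparing randomised arms are not affected at all.

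**What to change.** In Section 8.2:

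1. Add race/ethnicity and number of affected first-degree relatives to the six-term regression. Where reclassification defines the groups, also add the relevant baseline risk score (FRS for the coronary result, Diabetes Risk Score for the diabetes result). All are already collected.
2. Tabulate baseline characteristics by result group as well as by randomised arm.
3. Replace the sentence on eliminating baseline differences with wording such as: *Result groups are not randomised. The coefficients for dummies 1 and 2 are associations adjusted for the listed covariates. They are not effects of being told a result, because the arms without genetic testing are not genotyped.*

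The cost is a SAP wording change, about 4-5 degrees of freedom from roughly 106 people, and a more cautious conclusion. No new data collection is needed.

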8.2. Analysis Plan

Demographic characteristics of the sample (income level, age, gender, race/ethnicity, educational level) will be provided using descriptive statistics to describe the overall sample and by group to ensure that randomization was effective. Distribution of variables will be determined prior to further statistical analysis. SAS software (80) will be used for all analyses.

To address the primary aims, mixed models will be used. The first aim is to determine the direct and interactive effects of genetic risk information incorporated with standard CHD/T2D risk counseling and a health coaching intervention for CHD/T2D on behavior change (diet, physical activity) in AF primary care patients over 12 months. The goals of the statistical analysis will be to quantify: (1) the extent to which genetic risk counseling influences the trajectory of change in physical activity and diet measures from baseline to 3, 6, and 12 months; and (2) the extent to which the genetic risk information augments the trajectory of the effects of health coaching on diet and physical activity measures over the same time period. We will fit two general linear mixed models to these data (81), with

physical activity and diet measures at each of the five points in time. For either model, there will be three independent variables: genetic risk information (G) with values of 1 or 0, health coaching (HC), also with values of 1 or 0, and time since randomization, with values of 0, 3, 6, and 12 months. Within the context of the linear mixed model, we should observe a statistically significant three way interaction of time by genetic information by health coaching. The particular type of longitudinal model selected for analysis will depend upon preliminary analyses of the data. For example, a subject specific (also called hierarchical) model with random intercept and slope assumes that within subject variances increase or decrease over time. A model hypothesizing only a random intercept does not assume that within subject variances show this pattern. Another consideration will be the extent of missing data; some longitudinal models are better than others at handling missing data.

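### In the Aim 2 regression the dummy 1 and dummy 2 coefficients are differences in uncoached patients only, but Section 8.2 describes them without that condition

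*Combined protocol and SAP*

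**What the plan says.** Section 8.2 (Analysis Plan) of the combined protocol and SAP sets out a linear regression of 6-month diet or physical activity in the two genetically tested arms. The predictors are listed in one sentence: "There will be six independent variables: the outcome measured at baseline (a covariate), the results of the genetic testing (entered as two dummy coded variables"), then "a dummy coded variable to indicate the presence or absence of health coaching", then "two dummy coded variables representing the interaction of health coaching and the results of genetic testing".

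The risk dummies are defined explicitly: "dummy 1 will be 1 if the patient has ‘low’ risk based on number of risk alleles and zero otherwise", and "Dummy 2 will be 1 for patients with ‘high’ risk based on number of risk alleles and zero otherwise". Patients with both dummies at zero are the reference, meaning those whose result did not move their risk.

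The plan then interprets the coefficients. For low risk, "the regression coefficient for dummy 1 will reflect the differences in average adjusted outcome at 6 months" between patients moved down and patients not moved. For high risk, "the regression coefficient for dummy 2 will reflect differences in adjusted outcome means" between patients moved up and patients not moved. Neither sentence mentions coaching. The plan explains adjustment as removal of baseline differences in the outcome and nothing more. The interaction terms are given one job, which is to test whether these comparisons vary with coaching.

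**The concern.** Section 8.2 asks two questions of this regression. The first is whether behaviour change differs by how the genetic result shifted the patient's risk. The second is whether that difference depends on coaching. The plan offers the dummy coefficients as the answer to the first and the interaction terms as the answer to the second.

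Once the interaction terms are in the model, a dummy coefficient no longer summarises both arms. It describes the arm in which coaching is coded zero. An analyst who follows the text would report a difference estimated from SRA+GRC patients as though it described all tested patients. Any effect of the result among coached patients would be missing from that number.

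**Working it through.** **Inputs.** From Section 8.2: one baseline covariate, two risk dummies (D1 low, D2 high), one coaching dummy (HC) and two interaction terms. 1 + 2 + 1 + 2 = 6, which matches the stated count. HC is called dummy coded in this regression. The values are not printed there, but the mixed-model text in the same section gives "health coaching (HC), also with values of 1 or 0". The plan states no numerical result for this analysis, so there is none to reproduce.

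**Algebra.** The model is

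E[Y] = b0 + b1·baseline + b2·D1 + b3·D2 + b4·HC + b5·D1·HC + b6·D2·HC.

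- Low versus unaffected: b2 + b5·HC, so b2 if uncoached and b2 + b5 if coached.
- High versus unaffected: b3 + b6·HC, so b3 if uncoached and b3 + b6 if coached.
- Equal-weight average over coaching, low: 0.5·b2 + 0.5·(b2 + b5) = b2 + 0.5·b5. For high: b3 + 0.5·b6.
- Gap between average and coefficient: 0.5·b5 or 0.5·b6, which is zero only if the interaction is zero.

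If absence of coaching were coded 1 instead, b2 and b3 would be coached-only differences. The unconditional description would still be wrong.

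**Numerical check (effects assumed, not from the documents).** Low versus unaffected was set at −0.2 uncoached and +0.3 coached, and high versus unaffected at +0.1 and +0.5. The residual SD was 1, with 200 patients and a 30/40/30 low/unaffected/high split.

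| Coaching code | D1, no noise | D2, no noise | D1, mean of 2,000 simulations | D2, mean of 2,000 simulations |
|---|---|---|---|---|
| 0/1 | −0.20 | 0.10 | −0.200 | 0.093 |
| −0.5/+0.5 | 0.05 | 0.30 | 0.047 | 0.295 |

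The 0/1 coefficients return the uncoached differences. The centred coefficients return the averages.

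**Simple illustration (assumed).** With 0 SD uncoached and 0.5 SD coached, b2 = 0 and b5 = 0.5. The average is 0 + 0.5 × 0.5 = 0.25 SD.

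**Precision.** With n_L low and n_U unaffected patients per arm, the same in both arms, and in residual SD units:

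- variance of b2 = 1/n_L + 1/n_U;
- variance of the average = ¼ × 2 × (1/n_L + 1/n_U), which is half of that;
- SE ratio = √2, about 1.4, whatever the split.

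The absolute SEs need assumptions:

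- *106 patients, 25/50/25.* Section 5.1 gives 250 enrolled and Section 8.1 gives at most 15% attrition: 250 × 0.85 / 2 ≈ 106, or 53 per arm, with n_L = 13.25 and n_U = 26.5. The SE of b2 is √(1/13.25 + 1/26.5) = 0.336. The SE of the average is √(1/26.5 + 1/53) = 0.238. The split is assumed. Section 8.1 first gives its attrition figure over 12 months, whereas this outcome is at 6 months, so 106 is nearer a floor for 250 enrolled.
- *200 patients, 30/40/30.* Here 200 is the figure printed in Section 8.2 and the split is assumed. The simulated mean SEs are 0.245 and 0.174. The formula gives √(1/30 + 1/40) = 0.242 and 0.242/√2 = 0.171.

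**The case against.** The strongest reply is that nothing is lost. The six-term model holds all the information needed for the uncoached, coached and averaged differences, and the plan commits to examining the interaction. In the 0 and 0.5 SD illustration, the 0.5 is the interaction coefficient in the same output, so an attentive reader would see it. This stands in part: the effect would be hidden only from someone who reads the dummy coefficient as described and stops there. It does not rescue the description. Testing whether the comparisons vary with coaching does not tell the reader that the reported comparison belongs to one arm, and a non-significant interaction does not make b2 an average.

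Three stronger readings are tempting, and the documents do not support them.

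- *That the plan claims an overall effect in so many words.* It does not. Its wording is unconditional, and the fault is the missing condition.
- *That the trial's own hypothesis predicts this interaction.* The synergy described in Section 8.1 is between receiving genetic testing and receiving coaching, across the four arms. It says nothing about whether a low or high result matters more when coached. The documents give no direction or size for the result-by-coaching interaction.
- *That the doubled variance is efficiency lost.* The two SEs belong to different quantities. In the 0 and 0.5 SD illustration with 106 patients, the average is 0.25/0.238 = 1.05 SE. The interaction is 0.5/(√2 × 0.336) = 1.05 SE. The point is what is being estimated, not that the average is easier to detect there.

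It is also fair to say that an equal-weight average is a choice. If the effects have opposite signs in the two arms, it describes neither.

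**Conclusion.** The stated interpretation is wrong for both dummies. Each coefficient is a difference in SRA+GRC patients, and Section 8.2 presents it without that limit. No other part of the document corrects this, and no centring, least-squares mean or averaged contrast is specified for this model.

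Under 1:1 allocation the error equals half the interaction coefficient. That amount is unknown, and any figure for it is an illustration. The SE ratio of about 1.4 holds for any split if the arms are balanced. The absolute SEs (about 0.34 versus 0.24, or 0.245 versus 0.174 residual SD) rest on the assumed numbers and splits.

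The consequence is contained. A reader might infer that the regression is invalid or that the main results are compromised, but neither follows. The model is sound, and the primary mixed models and the sample size do not depend on these coefficients. The wording should be corrected before analysis, because as written it gives the wrong answer to this regression's first question unless the interaction is zero.

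**What to change.** Keep the six-term model and change Section 8.2 as follows.

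1. Reword both interpretation sentences to say that, with coaching coded 0/1, the dummy 1 and dummy 2 coefficients are the low-versus-unaffected and high-versus-unaffected differences in uncoached patients.
2. Prespecify b2 + 0.5·b5 and b3 + 0.5·b6 as the coaching-averaged differences. Coding coaching −0.5/+0.5 makes the dummy coefficients equal to these, in which case the first sentence is reworded to match.
3. Report the uncoached (b2, b3) and coached (b2 + b5, b3 + b6) differences with the averages, and state that the averages are read together with the interaction test.

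The cost is two sentences and a few contrast statements in SAS, which the plan already names. No new data are needed. The small downside is more reported quantities: three differences for two dummies and two outcomes make 12. The plan should say which are the main ones and that the rest are descriptive. If the team does not want an average, the minimum correction is to label the coefficients as uncoached-only and add the coached differences.
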